#### **8.4.2 Secondary Endpoint(s)**

Immune responses over time for ELISPOT and ELISA are secondary endpoints as are peripheral PAP-specific T cell immune response to sipuleucel-T over time via a T cell stimulation index from a proliferation assay, and cytokine production by Luminex assay. Additionally, responder analyses by time point will be performed for the data generated from the proliferation assays, ELISPOT, and ELISA. A positive response will be defined as having a post-baseline result exceeding a threshold value, determined on the basis of baseline and historical sipuleucel-T data, that ensures a sufficiently low false positive rate (i.e., 5% or less) for each immune response parameter. The threshold will be antigen and assay dependent.

Time to PSA progression is defined as: 1) the time from randomization to PSA progression, and 2) the time from first enzalutamide treatment to PSA progression. Those subjects who do not experience PSA progression will be censored in the analysis at the date of their last PSA assessment. PSA progression, based on the randomization date (i.e., definition 1) will be defined for those subjects who experience a decline in PSA compared to baseline as the date that a 25% or greater increase in PSA and an absolute increase of 2 ng/mL or more from the nadir is documented, which is confirmed by a second value obtained 3 or more weeks later (Scher 2008). For those subjects who do not experience a decline in PSA compared to baseline, PSA progression is defined as the date a 25% or greater increase from the baseline value along with an increase in absolute value of 2 ng/mL or more after 12 weeks of enzalutamide treatment (Scher 2008). PSA progression based on the first enzalutamide treatment (i.e., definition 2) will be defined in a similar manner except the most recent PSA value prior to the first enzalutamide treatment will be used as the baseline value.

PSA progression time, based on the randomization date, will be calculated as follows for those subjects with PSA progression:

$$\text{Progression time (days)} = [(\text{PSA progression date}) - (\text{randomization date})] + 1.$$

PSA progression time, based on the randomization date, will be calculated as follows for subjects who are censored:

$$\text{PSA progression time (days)} = [\text{last PSA assessment date} - (\text{randomization date})] + 1.$$

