### **8.5.3 Efficacy Analyses**

The primary efficacy analysis will consist of a repeated measurement analysis of immune response over time evaluated using PA2024-stimulated T cell proliferation via tritiated-thymidine uptake based on the immune response population. The logarithm of response will be used for analysis. Fixed effect terms in the model will include treatment arm, visit as a class effect, and treatment by visit interaction. The correlation of responses across time within a subject will be modeled using several candidate variance-covariance structures including unstructured, compound symmetry, heterogeneous compound symmetry, autoregressive (1), and heterogeneous autoregressive (1). The variance-covariance structure providing the smallest Bayesian information criteria will be selected for the final model. Fixed effect terms in the model will be tested for significance using type III sums of squares. The formal test for difference between the treatment arms will be based on the p-value for the treatment arm effect unless a significant treatment by visit interaction ( $p < 0.05$ ) is observed, in which case by-visit treatment comparisons will be made using appropriate contrast statements. Estimates of treatment effect and corresponding 95% confidence intervals (CIs) will be provided on the ratio scale obtained by exponentiation of the model derived treatment effect and CI on the logarithm scale. Immune responses over time for other assays will be analyzed using identical methods described for the primary efficacy analysis except for the ELISPOT, which will be analyzed using ranks instead of on the logarithm scale.

The response rate for each assay and for each antigen will be compared between treatment arms at each visit using Fisher's exact test based on the immune response population. In addition, analyses will be performed modeling response rates over time using appropriate methods to account for the correlation of responses over time within a subject.

Time to PSA progression will be compared between the treatment arms using a Cox regression model with terms for treatment, baseline PSA (logarithm scale), and baseline LDH (logarithm scale) in the model based on the ITT population. The estimated HR of the treatment effect and

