After 52 weeks of enzalutamide treatment provided by Dendreon, subjects in either treatment arm may continue to receive enzalutamide obtained from other sources at the discretion of their treating physician. Dendreon cannot provide enzalutamide beyond the protocol-specified duration of 52 weeks.

All subjects will receive a total of 52 weeks of enzalutamide. The active phase will begin at registration and continue through the post-treatment visit (30 to 37 days following the last study

treatment). The long term follow-up (LTFU) phase will begin after the post-treatment visit and will continue until the subject's death or until Dendreon terminates the study.

All immune monitoring (IM) endpoints will be collected from all subjects who receive at least one infusion. Cellular and serological peripheral immune responses will be assessed for subjects in both arms. In both arms, IM blood samples will be collected at baseline (screening); pre-leukapheresis 2 and 3; and weeks 6, 10, 14, 20, 26, 40, and 52, with the timing of visits based on the date of the first sipuleucel-T infusion (Day 0).

During the Active phase, safety assessments in both arms will include AE monitoring, laboratory tests (complete blood count (CBC) collection serum chemistries, and liver function tests [LTFs]), vital signs, Eastern Cooperative Oncology Group (ECOG) performance status, anticancer therapies, first opioid use for cancer-related pain, PSA monitoring, and physical examinations.

During the LTFU phase, safety (treatment-related AEs, cerebrovascular events, and seizures), survival status, PSA, ECOG performance status, first opioid use for cancer-related pain (if applicable), and anticancer therapies will be assessed every 3 months until the subject's death or until Dendreon terminates the study.

Sponsor's decision to terminate the study: During the first quarter of 2017, a decision was made to terminate the study during 2017 after at least 3 years of follow-up data was collected on all subjects participating in the study and still being followed. The end of follow-up period was defined as 3 years after the date that the last enrolled subject received the last infusion of sipuleucel-T.

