4.2 Immune Response

To evaluate the magnitude of peripheral immune response over time as determined by the following:

- Peripheral PAP-and PA2024 specific T cell immune response to sipuleucel-T over time via T cell stimulation index from a proliferation assay.
- T cell interferon-gamma (IFN- γ) enzyme-linked immunospot (ELISPOT) response to PA2024 and PAP
- Humoral response by enzyme-linked immunosorbent assays (ELISA) to PA2024 and PAP
- Chemokine and cytokine production via fluorescent immunoassay (MesoScale Discovery assay system).

The PAP and PA2024 IFN γ ELISPOT response over time will be compared between the Concurrent Arm and the Sequential Arm, beginning with the immune sample taken at the baseline, using a repeated measurement mixed model analysis stratified by screening PSA levels and screening lactate dehydrogenase. The unit of analysis will be the background subtracted counts, computed as the median count of 3 wells exposed to antigen minus the median count of 3 wells exposed to media alone. The background subtracted counts will be ranked prior to analysis. The model will include treatment and visit as fixed effects as well as treatment by visit interaction, subject as random effect, and the two stratification factors at randomization as covariates. Visit will be considered as a categorical variable for the modeling. Several variance-covariance structures will be investigated to determine which model fit is best based on the model with the lowest Bayesian Information Criteria (BIC). Variance-covariance structures that will be investigated are unstructured (UN), auto-regressive (1) AR(1), heterogeneous autoregressive (1) (ARH (1)), compound symmetry (CS), and heterogeneous compound symmetry (CSH). Comparisons between the treatment arms at specific timepoints visits will be made using a linear contrast statement. A proper transformation (such as log-scale or rank transformation) will be applied if the data are not normally distributed. A secondary analysis of this endpoint will be based on a categorical response/no response basis. Categorical response will be defined on the basis of a threshold value determined from PA2024 ELISPOT background subtracted counts measured at baseline that ensures a sufficiently low false positive rate (i.e., 5% or less). The two treatment arms will be compared using a Fisher's exact test for a response at any time point post-baseline and by time point.

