The T cell proliferation in response to PAP and PA2024, and PAP and PA2024 humoral responses of both arms will be compared using methods as described for the PA2024 ELISPOT response for IFN- γ . The unit of analysis for the T cell proliferation data is the stimulation index, defined as the median ^3H uptake of 3 wells exposed to antigen divided by the median ^3H thymidine uptake of 3 wells exposed to media. The stimulation index will be log-transformed prior to analysis. The unit of analysis for the humoral response data is the antibody titer, which will be log-transformed prior to analysis. In addition, the responder rate will be summarized by time point for the data generated from the proliferation assays, ELISPOT, and ELISA. A responder at a time point is a subject with a post-baseline result at the time point exceeding the 95th percentile at baseline.

AIM-V Cytokine data will be collected after each infusion of sipuleucel-T. Each cytokine parameter over time will be compared between the Concurrent Arm and the Sequential Arm, using a repeated measurement mixed model analysis. The same modeling strategy as outlined for PA2024 ELISPOT response for IFN- γ will be applied to the AIM-V cytokine data. Comparisons between treatment arms at specific time points will be made using a linear contrast statement. The data will be analyzed on a log-scale with a count of 1 added prior to taking the log so that the log will always be defined. Serum cytokine data will be analyzed in a manner similar to the AIM-V cytokine data.

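### The 5% false-positive rate of the SAP's responder threshold holds for one sample and does not carry over to response at any of nine post-baseline time points

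*SAP*

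**What the plan says.** SAP 4.2 adds a responder analysis to the ELISPOT model. The threshold comes from baseline background-subtracted counts and is one "that ensures a sufficiently low false positive rate (i.e., 5% or less"). The next sentence compares the two arms by Fisher's exact test "for a response at any time point post-baseline and by time point".

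The same section extends the ELISPOT methods to T cell proliferation and to humoral response by cross-reference. For by-visit summaries it fixes the cut-off: "A responder at a time point is a subject with a post-baseline result at the time point exceeding the 95th percentile at baseline".

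On sampling, SAP section 1 states: "IM blood samples will be collected at baseline (screening); pre-leukapheresis 2 and 3; and weeks 6, 10, 14, 20, 26, 40, and 52". That is nine post-baseline samples. Table 1 of the protocol also marks the 100 mL sample at the post-treatment visit, which would make ten.

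The protocol's plan differs. Section 8.4.2 says: "Additionally, responder analyses by time point will be performed for the data generated from the proliferation assays, ELISPOT, and ELISA". Section 8.5.3 specifies Fisher's test at each visit and adds that "analyses will be performed modeling response rates over time using appropriate methods to account for the correlation of responses over time within a subject". The SAP has no such response-rate model, and the protocol has no any-time comparison.

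**The concern.** A threshold at the baseline 95th percentile gives a subject with no immune response a 5% chance of exceeding it on one later sample. If one exceedance among nine samples makes the subject a responder, that chance accumulates. Neither document recalibrates the threshold for this definition, and the SAP places the 5% statement directly before the any-time comparison.

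Two things are at stake. Any-time responder rates will include more false responders than 5% suggests, in both arms, which shrinks the apparent difference between concurrent and sequential treatment. The false-response chance also depends on how many samples a subject contributes, so the definition is sensitive to differences in follow-up between arms.

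**Working it through.** **Inputs.** Per-sample false-positive rate 5% (SAP 4.2). Nine post-baseline samples (SAP section 1). 25 and 27 subjects (SAP 3.1). Nominal significance level 0.05 (SAP 4.7.2). The within-subject correlation is not given. SAP 4.2 says only that "Several variance-covariance structures will be investigated to determine which model fit is best", so the correlation is varied here as an assumption.

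**1. The plan's own figure.** For one sample, 1 - 0.95^1 = 5.0%. The stated rate reproduces per time point.

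**2. Any of k samples.** If samples are independent, the chance is 1 - 0.95^k. For k = 9 this is 1 - 0.630 = 37.0%. For normal values with exchangeable correlation ρ and c = 1.645, the chance is 1 - ∫ φ(u) Φ((c - √ρ·u)/√(1-ρ))^k du:

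| ρ | 3 samples | 9 samples | ratio |
|---|---|---|---|
| 0 | 14.3% | 37.0% | 2.6 |
| 0.3 | 13.0% | 28.8% | 2.2 |
| 0.5 | 11.8% | 23.3% | 2.0 |
| 0.7 | 10.3% | 17.7% | 1.7 |
| 0.9 | 8.0% | 11.2% | 1.4 |
| 0.95 | 7.1% | 9.1% | 1.3 |

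At ρ = 0.99 the nine-sample figure is 6.7%. Under AR(1), one of the structures the SAP lists, it is 30% at 0.5 and 15.5% at 0.9 (simulation). With ten samples the range for exchangeable ρ of 0 to 0.9 is 40.1% to 11.6%. If the 95th percentile is itself estimated from about 52 baseline values, the nine-sample range is about 44% to 14% (simulation).

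**3. Size of the between-arm test, equal sampling.** Exact enumeration of Fisher's test at 25 versus 27 gives a size of 2.6%, 3.3%, 3.7% and 3.9% when the common false-responder rate is 11%, 20%, 30% and 37%. It does not exceed 5%.

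**4. Dilution.** If a fraction p truly respond and are always detected, the observed rate is p + (1-p)f, where f is the false-responder rate. The observed difference is therefore the true one times (1-f). Take assumed true rates of 20% and 60%:

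| f | observed rates | difference | power |
|---|---|---|---|
| 5% | 24% vs 62% | 38 points | 77% |
| 11% | 29% vs 64% | 36 points | 69% |
| 23% | 39% vs 69% | 31 points | 55% |
| 37% | 50% vs 75% | 25 points | 42% |

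**5. Unequal sampling.** Three samples is the scheduled minimum for a concurrent-arm subject in the immune response population (three infusions and at least 10 weeks of enzalutamide, SAP 3.2.1). Enzalutamide starts 2 weeks before the first leukapheresis, so such a subject can qualify about 7 to 8 weeks after the first infusion, with pre-leukapheresis 2 and 3 and week 6 drawn. In the sequential arm enzalutamide starts at about week 10, so qualification comes at about week 20, with five or six samples. The size of Fisher's test with no true response, 25 versus 27, is:

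| ρ | one arm all 3, other all 9 | half of one arm 3, all others 9 |
|---|---|---|
| 0 | 40% | 11.8% |
| 0.3 | 21% | 7.0% |
| 0.5 | 12% | 4.9% |
| 0.7 | 5% | 3.3% |
| 0.9 | 2% | 2.1% |

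The first column is an extreme bound. If only 20% of one arm has three samples, the size is at most 5.2%.

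**The case against.** The SAP can be read as attaching 5% to the threshold, and so to one result, where it is correct. Protocol 8.4.2 reads that way, and the SAP's later definition is for a responder at a time point. Allowing 5% or less also permits a stricter ELISPOT cut-off. This stands to the extent that the 5% is not a false figure. What is missing is any statement that it does not apply to the any-time definition in the next sentence.

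A reader might infer that the comparison between arms has an 11-37% false-positive rate. The documents do not support that. The inflated quantity is the chance that a non-responding subject is called a responder. With equal sampling it is the same in both arms, and Fisher's test stays below 5%.

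A reader might also infer that attrition biases the test. No passage shows unequal attrition. Under protocol 4.3.2, subjects who stop enzalutamide after three infusions and at least 10 weeks of it stay on the active-phase schedule. Progression does send subjects to long-term follow-up (protocol 4.5), where Table 1 marks no immune samples. The two arms also reach the 10-week mark at different visits. Unequal sampling is therefore possible, but the calculation shows that it must be large, with low to moderate correlation, before the level is lost.

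Finally, SAP section 4 makes all tests exploratory, and SAP 4.2 calls the responder analysis secondary to a mixed model that uses no threshold. That limits the consequence and does not remove the mismatch.

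**Conclusion.** The point holds for the responder definition. Over nine scheduled samples, the chance that a non-responding subject is called an any-time responder exceeds 5% at every correlation examined. It is 37% down to 11% for exchangeable correlation of 0 to 0.9, assuming exactly 5% per sample and complete sampling. Neither end is a bound: the figure is about 9% at 0.95, and higher than 37% if a tenth sample counts or the threshold is estimated from the trial's own baselines.

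The likely harm is overstated responder rates and a diluted contrast. Loss of type I error control is conditional on substantial imbalance in samples per subject together with low to moderate correlation. The missing response-rate model is a separate departure from protocol 8.5.3, and restoring it is the natural remedy. The overall impact is modest given the exploratory status of the tests.

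**What to change.** In SAP 4.2:

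- State that the 5% rate applies per time point, and keep the by-visit Fisher tests.
- Restore the protocol 8.5.3 model of response rates over time as the overall responder comparison, for example GEE or mixed logistic regression with arm and visit. This estimates response rates across visits, which is a different question from ever having responded, and the SAP should say so.
- For the any-time definition, do one of two things. Either calibrate its threshold on the maximum over visits (under independence, 5% over nine samples needs 1 - 0.95^(1/9) = 0.57% per sample), or report the any-time rate descriptively only. In the second case, give samples per subject by arm and the expected false-responder rate under stated correlation assumptions.

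The cost is SAP wording and one extra model in about 52 subjects, where a repeated binary model will be imprecise. No new data are needed.

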4.3 PSA

PSA data, including change from baseline and percent change from baseline, will be summarized descriptively by treatment arm at each time point. For each time point where change from baseline is evaluated for continuous variables, descriptive statistics will be displayed for the values at baseline, values at the time point, values for change from baseline, and percent change from baseline at the time point for the set of subjects who have data at both baseline and the time point being assessed. Additionally, the maximal percent decline of serum PSA from baseline at any time point will be summarized using waterfall plots and will be compared between the treatment groups using a Wilcoxon test. Baseline will be defined as the pre-randomization PSA value. The percent of subjects with a 50% or more maximal decline in PSA at any post-baseline time point will be compared between the treatment arms using a Fisher's exact test.

Time to PSA progression will be compared between the treatment arms using a Cox regression model with terms for treatment, baseline PSA (logarithm scale), and baseline LDH (logarithm scale) in the model based on the ITT population. The estimated HR of the treatment effect and its 2-sided, 95% CI, using the sequential arm as the denominator will be provided. The percentage of subjects free of PSA progression with an associated 95% CI at landmark time points such as 6 and 12 months will be provided by treatment arm as well as pooled over treatment arms using the Kaplan-Meier method.

Time to PSA progression is defined as: 1) the time from randomization to PSA progression, and 2) the time from first enzalutamide treatment to PSA progression. Those subjects who do not experience PSA progression will be censored in the analysis at the date of their last PSA assessment. PSA progression, based on the randomization date (i.e., definition 1) will be defined for those subjects

who experience a decline in PSA compared to baseline as the date that a 25% or greater increase in PSA and an absolute increase of 2 ng/mL or more from the nadir is documented, which is confirmed by a second value obtained 3 or more weeks later (Scher 2008). For those subjects who do not experience a decline in PSA compared to baseline, PSA progression is defined as the date a 25% or greater increase from the baseline value along with an increase in absolute value of 2 ng/mL or more after 12 weeks of enzalutamide treatment (Scher 2008). PSA progression based on the first enzalutamide treatment (i.e., definition 2) will be defined in a similar manner except the most recent PSA value prior to the first enzalutamide treatment will be used as the baseline value.

4.4 Overall survival

Overall survival is defined as the time from randomization to death due to any cause. Subjects will be followed for survival for 3 years from the date of randomization. Those subjects alive at study end will be censored in the analysis at the day of their last documented visit or contact date. Overall survival time will be calculated as follows:

- For subjects who died prior to the study end:
 - Survival time (days) = [(death date) – (randomization date) + 1]
- For subjects who did not die prior to the study end or whose death status is unknown:
 - Survival time (days) = [(last contact date) – (randomization date) + 1]

Overall survival will be compared between the two arms using a stratified log-rank test. The estimated adjusted hazard ratio of the treatment effect and its 2-sided 95% CI, using the sequential arm as the reference group, will be generated using a Cox regression model adjusted for baseline PSA (natural log scale) and baseline LDH (natural log scale). Median survival and survival rates at specific time points will be estimated for each treatment arm using the Kaplan-Meier method, with corresponding 95% CIs.

4.5 Safety

Safety data will be summarized descriptively in aggregate within the safety population. All AEs observed through the post-treatment visit will be summarized. Following the post-treatment visit, only new treatment-related AEs, SAEs, seizures, and CVEs (regardless of causality) through the end of the study will be recorded and summarized. No formal statistical testing is planned for any safety summaries.

4.5.1 Adverse Events

Adverse events (AEs) will be summarized and listed by treatment group and by the Medical Dictionary for Regulatory Activities (MedDRA) preferred term within each system organ class using the most current version of MedDRA at the time of study closure. Summary tables will include all AEs reported in the Concurrent Arm and Sequential Arm from the first leukapheresis.

Tables/listings to be produced will include the following:

- Incidence within system organ class (MedDRA)
- Incidence by preferred term and decreasing frequency
- Incidence by NCI CTCAE (Version 4.03) severity grade, by decreasing frequency
- Incidence of Adverse Events Occurring ≤ 1 Day After Infusion by preferred term and decreasing frequency
- Incidence of \geq Grade 3 AEs, by preferred term and decreasing frequency
- Incidence of AEs that led to premature discontinuation of study therapy or study
- Incidence of SAEs within system organ class (MedDRA)
- Incidence of SAEs by preferred term and decreasing frequency
- Incidence of Cerebrovascular Adverse Events by preferred term and decreasing frequency

Adverse events that occur multiple times for a subject will be counted only once per subject in incidence summary tables. In tables that enumerate AEs by severity, only the worst severity for an AE occurring multiple times for a patient will be counted.

No formal statistical testing is planned for the above AE summaries. A 2-sided Fisher's exact test may be used to assess any potential trend, if appropriate, and be interpreted as hypothesis generating.

